Partners Human Research Committee Detailed

Protocol

Protocol title: Using mHealth technology to identify and refer surgical site infections in Rwanda.

Version Date: 9/20/2017

BACKGROUND AND SIGNIFICANCE:

Surgical site infections (SSI) are a major source of morbidity and mortality worldwide and the leading health-care-associated infection in the developing world.¹ The burden is disproportionately felt in low- and middle-income countries (LMICs)² and especially in Africa, where the rate of post-operative SSI has been documented as high as 30.9%.³ In these settings, SSIs often develop after patients are discharged from care,² and geographic and financial barriers can prevent patients from following up during the post-operative period.^{4,5} One study from the Central African Republic reported that only 25% of surgical patients returned for their 30-day post-operative follow-up visit.⁶ Failure to return or a delayed return to care among patients with SSI is linked with poor health outcomes, including sepsis, need for re-operation, and death,⁷ and an increase in healthcare costs.

In many LMICs, community health workers (CHWs) play a major role in delivering household-based care to vulnerable populations who might otherwise be unable to access health facilities. These CHWs are typically lay individuals nominated by their communities with relatively low levels of education and training.⁸ In Rwanda, villages typically have three CHWs: two “binomes” who are trained to provide care for malaria, pneumonia, and diarrhea for children⁹ and a third CHW responsible for maternal health.¹⁰ These CHWs are considered a critical component of the health system in a country that has seen a 59.5% decline in maternal mortality and 70.4% decline in under-five mortality since 2000.¹¹ In some limited geographic areas, CHWs are engaged in other health activities. For example, CHWs provide support for HIV patients, leading to improved treatment adherence and patient outcomes.^{12,13}

The current Rwandan CHW network includes 45,000+ lay health workers who focus on basic health screening and education for pre- and post-partum women and children under-five years. The lack of professional training of the existing CHWs, combined with the large number of activities already included in their daily work, limits their ability to provide more complex care, such as monitoring post-operative patients.

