Through PIH, we will hire four sCHWs with similar demographics to the existing CHWs specifically for this study. They will receive five days of training on the organization of the Rwandan health sector, post-operative follow-up, operation of the mHealth tools, best practices in wound photography, and basic SSI physiology and identification. The five-day training is similar in length to the specialized health trainings current CHWs receive and mirrors the training experience of sCHWs in the pilot project in Haiti. The mHealth tool was developed by Sana and is administered on a Samsung Galaxy X-Cover 2 smart phone. The tool prompts the CHW to evaluate the wound for 1) warmth, 2) increased pain, 3) swelling, 4) firmness of the wound, 5) wound opening, and 6) fluid drainage and quality. The phone also has the capability to take a photo of the wound and record GPS location.

PHASE 1:

During this phase, we will address Aim 1, optimization of the SSI screening protocol. The protocol will be piloted using the mHealth device among a cross-section of patients receiving surgery at Kirehe District Hospital (KDH), Rwanda. We will also embedded Specific Aims 2 and 3 (assessments of antibiotic prescribing practices and WASH resources) into this phase.

Consenting participants will be screened for surgical site infection (SSI) 10 days' post-operation. The screening window will be ± 3 days (7-13 days post-operation). During the screening visit, patients will be evaluated in two different steps. First, a GP will perform a clinical assessment. These data will be considered the gold standard against which to compare the SSI screening protocol. Secondly, the patient will be independently screened by a sCHW who will use the mHealth tool described above to administer the six basic screening questions.

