For consenting participants that are discharged prior to their 10-day post-operative screening, a study data collector will administer a simple self-report survey to collect basic patient demographic and socioeconomic characteristics on the day of discharge. They will be asked to return to the clinic for screening. In line with national policies, these participants will receive a voucher worth approximately US \$10, to compensate for travel and time, to return to the clinic. The voucher will be redeemed when the patient arrives to their assigned screening day. If a participant misses his assigned screening day, the participant will be contacted via his local community health worker.

Consenting patients that are not discharged prior to their 10-day post-operative screening will have demographic and socioeconomic data collected via self-report survey administered by the

study data collector as well as GPs and sCHW conducting the physical examination on the assigned screening day. These participants will not receive any voucher. Study staff will also extract clinical data from the patient files of all consenting participants.

[figure not shown]
We anticipate enrolling a minimum of 525 post-operative patients during the five-month period. With an estimated overall SSI rate of 15% based on existing literature and 10% loss-to-follow-up (LTFU), we expect 71 patients will have a GP-diagnosed SSI and 402 patients will not have a GP-diagnosed SSI.

PHASE 2:

After the screening protocol has been optimized in phase 1, new patients receiving c-section surgery at KDH will be enrolled and randomized to one of three study arms. Rates of return and severity of SSI at return across the three arms will be compared (Aim 4). We will also report process indicators to describe the implementation of the CHW-mHealth interventions (Aim 5). For patients that have contact with a sCHW (Arms 1 and 2), and are suspected to have a SSI and referred back to care but fail to return, we will assess their barriers to care (Aim 6). For patients that have no special follow-up, we will assess their post-operative follow-up practices (Aim 7). Embedded in this study will be a small sub-study on the costs of care and impact of these costs on family expenses (Aim 8).

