Specific Aim 1: During the follow-up screening visit, patients will be evaluated in two different steps. First, the patient will be screened by a CHW who will use the mHealth tool to administer the basic screening questions. The mHealth application will prompt the CHW to evaluate for warmth, increased pain, increased swelling, increased firmness of the wound, wound opening, and fluid drainage and quality. The CHW will take photo of the wound on the mHealth tool. Second, a GP will perform a clinical assessment and provide responses to two basic questions: 1) Do you diagnose the patient as having an SSI? And 2) Do you identify any other post-operative

complications that would warrant the patient's return to the clinic for physician review? These data will be considered the gold standard against which to compare the SSI screening protocol. The GP will also comment on the 6 characteristics from the mHealth tool for comparison.

Specific Aim 2: For one month of Phase 1, study nurses will observe the clinical interactions with patients during rounding and document in a case observation form (Appendix B) the prescription and taking of antibiotics during admission and at discharge.

Specific Aim 3: To assess the WASH infrastructure at the hospital, data collectors will administer a hospital assessment form (Appendix C). To assess variability, the data collectors will administer an abbreviated version of this form every 4 hours over the course of one week. At the follow-up visits, mothers will be asked about the access to sanitation facilities at home.

Analysis and Outcomes:

Aim 1:

Patients who are still admitted at the follow-up will be excluded from the developing of the screening algorithm. At 4 months into Phase 1, we will assess the validity of the SSI screening protocol. In this first assessment we will identify a cutoff (c) by optimizing the area under the receiver operating characteristic curve. We will consider the screen positive if the patient meets at least c of the 6 criteria. If the sensitivity of SSI screening protocol is less than 90% or the specificity is less than 80%, we will modify and optimize the screening protocol. Steps for modifying the algorithm include the following:

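### Aim 3 asks about home sanitation only at the Phase 1 day-10 visit, so women who do not return have no data, although a survey already reaches them before that visit.

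*Combined protocol and SAP*

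**What the plan says.** Aim 3 is to describe water, sanitation and hygiene (WASH) resources at the hospital and in the mothers' homes, and Study Procedures places it in Phase 1. For the homes, Biostatistical and Qualitative Analysis (Phase 1, Specific Aim 3) gives one time point: "At the follow-up visits, mothers will be asked about the access to sanitation facilities at home". The Phase 1 follow-up visit is the single screening at day 10, with a window of days 7 to 13. No other section collects this item at another time.

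Under Study Procedures, Phase 1, women discharged before day 10 are surveyed earlier: a data collector "will administer a simple self-report survey to collect basic patient demographic and socioeconomic characteristics on the day of discharge". The Phase 1 analysis section and the Data Safety section place this survey at enrollment instead; either way it precedes the return visit. Its listed socioeconomic items are household income, land ownership and transport cost as a barrier. Sanitation is not among them. Women still admitted at day 10 are surveyed and examined in hospital on the screening day.

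On expected attendance, the same section says: "With an estimated overall SSI rate of 15% based on existing literature and 10% loss-to-follow-up (LTFU), we expect 71 patients will have a GP-diagnosed SSI", with 402 expected not to have one. The Aim 3 analysis reports home WASH as frequencies and proportions with 95% confidence intervals. It says nothing about women who were not seen.

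**The concern.** Home sanitation is a household characteristic that a mother can report before she leaves hospital. Nothing about it requires waiting until day 10. Asking only then makes the availability of the answer depend on whether she returns.

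The protocol itself gives reasons why return may not be random. Background and Significance says that "geographic and financial barriers can prevent patients from following up during the post-operative period", and Potential Benefits describes transport cost as a known barrier. Remote or poorer households may also have worse sanitation. If so, the returners' proportion overstates access, and an ordinary binomial interval does not show it. What is at stake is the accuracy of the home component of a descriptive aim. The screening algorithm and the Phase 2 comparison do not use it.

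**Working it through.** **Inputs from the documents.** Planned Phase 1 enrollment 525, loss to follow-up 10% and SSI rate 15% (Study Procedures, Phase 1). No sample size is stated for Aim 3.

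**Inputs assumed.** The difference *d* in sanitation access between returners and non-returners is not in the documents; it is varied from 10 to 40 points. The proportion with access is also not given; 0.5 and 0.7 are used.

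1. **The plan's own figures.** Seen at follow-up: 525 × 0.90 = 472.5. With SSI: 472.5 × 0.15 = 70.9, or 71. Without: 472.5 × 0.85 = 401.6, or 402. The total is 71 + 402 = 473, so the stated figures reproduce.

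2. **Women without home data.** 525 × 0.10 = 52.5, about 52.

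3. **Bias from non-return.** Bias = missing share × *d*. At 10% missing:
   - *d* = 10 points: 0.10 × 10 = 1 point
   - *d* = 20 points: 2 points
   - *d* = 30 points: 3 points
   - *d* = 40 points: 4 points

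4. **Comparison with the interval.** Half-width = 1.96 × √(p(1 − p)/n). At n = 472.5 this is 4.5 points for p = 0.5 and 4.1 points for p = 0.7.

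5. **Effect on coverage.** Take a true proportion of 0.70. The returners' proportion is r = 0.70 + 0.10*d*, its standard error is √(r(1 − r)/472.5), and b = bias / standard error. Coverage is Φ(1.96 − b) − Φ(−1.96 − b). For *d* = 20 points: r = 0.72, standard error = 0.0207, b = 0.97, coverage about 84%. For *d* = 10, 30 and 40 points, coverage is about 92%, 69% and 49%.

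6. **Bounds without assuming *d*.** If 70% of returners have access and 10% of women are missing, the overall proportion lies between 0.90 × 0.70 = 63% (no non-returner has access) and 63% + 10% = 73% (all do).

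7. **If loss exceeds the plan (assumed).** At 20% missing the same differences give a bias of 2 to 8 points; at 30%, 3 to 12 points.

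8. **After the fix.** With up to 525 respondents the half-width at p = 0.5 is 1.96 × √(0.25/525) = 4.3 points, against 4.5. The precision gain is trivial.

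**The case against.** The strongest case against the point is that the selection may be weak and little depends on it. The statement on barriers is general background, not evidence about the Phase 1 visit. Phase 1 addresses those barriers directly, with a voucher of about US $10 for travel and time and contact through the local community health worker after a missed screening day. A fixed-value voucher might matter most to poorer women, which could shrink or even reverse the difference. Aim 3 has no hypothesis, sample size or decision rule. Distance, income, land ownership and transport cost are already collected before the visit, so returners and non-returners could be compared without changing a form.

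Much of this stands. The direction and size of the bias are not established, and the mitigating measures should be acknowledged. The core point remains for three reasons. The 10% loss is what the plan expects with those measures in place. The voucher is redeemed only on arrival, and the plan does not say that sanitation will be asked when a health worker makes contact. A comparison on income or distance would describe the selection without recovering the missing answers.

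A reader might also infer that moving the question yields a complete home WASH dataset of 525 women free of bias. The documents do not support that. The survey may have refusals or unanswered items. The stated home question covers sanitation only, so moving it does not supply water or hygiene data. Mahama Refugee Camp residents contribute hospital data but are not asked to return (Subject Selection and Enrollment, Phase 1), and the documents do not say whether the 525 or the 10% counts them.

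**Conclusion.** The point holds as a low-cost improvement to a descriptive aim. At the planned loss, about 52 of 525 women would lack a home sanitation answer that could have been obtained earlier. The reported proportion may be biased, probably upward. Under assumed differences of 10 to 40 points the bias is 1 to 4 points, within the half-width of about 4.5 points at p = 0.5.

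A reader might infer that the non-returners are known to be the poorest and most remote, or that the estimate is certainly too high. The documents contain no sanitation data and no comparison of returners with non-returners, so that is only a plausible inference from the stated barriers. The size rests on the assumed difference and on loss staying at 10%; it would grow if more women failed to return.

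**What to change.** In the Phase 1 text for Specific Aim 3, move the home sanitation questions to the self-report survey given before the return visit, for all consenting Phase 1 women. For women still admitted at day 10, ask them in the screening-day survey. In the Aim 3 analysis, define the home denominator as all survey respondents. Report Mahama Refugee Camp residents separately, or state whether they are included, because an earlier question could bring them into the estimate and change its population.

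The cost is a few more questions on an existing survey. No new visit or form is needed, and Aim 1 is unaffected.

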Specific Aim 8: We will assess the direct and indirect costs incurred by the mother and her family, stratified by whether or not she has a surgical site infection, and describe the burden of these costs relative to the overall financial expenditures of the household.

SUBJECT SELECTION AND ENROLLMENT:

This study will follow patients who received cesarean-section surgery at KDH and reside in Kirehe District. KDH is a 145-bed facility operated by the Rwanda Ministry of Health (RMOH) and supported since 2005 by the medical non-profit organization Partners In Health (PIH). The hospital serves a catchment area of 364,000 people, primarily residing in rural, outlying villages. In preliminary work, we conducted a chart review that showed that 7.3% of obstetric surgical patients and 3.1% of non-obstetric surgical patients returned to the hospital with an SSI. Based on regional literature, we expect the true rate of SSI in patients receiving surgery KDH to be 10-20%.²²

Phase 1

Participants will be adult (≥ 18 years) patients receiving cesarean-section surgery at KDH over a seven-month enrollment window. All patients receiving a cesarean section (c-section) surgery at KDH who reside in Kirehe district will be eligible and will be invited to participate on post-operative day 2. We anticipate enrolling 525 post-operative c-section patients who received surgery at KDH during the seven-month period. Patients will be enrolled consecutively. We will include patients from Mahama Refugee Camp when collecting information about the hospitalization and outcomes. However, these patients will not be asked to return for follow-up.

Phase 2

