1. Adding, removing or modifying questions. We will use a classification and regression tree (CART) analysis to determine the best set of individual or combined items from the initial screening questions. We will develop maximal trees with all six screening questions, and then apply reduced error pruning, removing questions that do not reduce predictive error by 10%. We will choose optimal trees based on overall predictive properties of the pruned tree. If the optimal tree removes screening questions, we will propose new questions guided by a) Rwandan colleagues for contextual relevance and b) global surgery and infectious disease experts for subject matter input.
2. Adding photo functionality with review by the GP. Email through the cellular network and uploading through the mHealth system could allow sCHWs to send a photo along with the screening question responses to a GP for their recommended diagnosis. If the SSI screening protocol is performing sub optimally, then we will explore the validity of the protocol with the photo and GP photo assessment added.

After 3 additional months (7 months into Phase 1), we will identify a new cutoff and reassess the sensitivity and specificity, with 95% confidence intervals, of the SSI screening protocol. This final algorithm will be considered optimal for Phase 2.

Aim 2:

We will describe the type of antibiotics prescribed, the median number of doses and amount of doses with interquartile ranges.

Aim 3:

We will describe the overall WASH infrastructure, variability in availability in WASH infrastructure and availability of WASH infrastructure in the mothers' homes using frequency and proportions with 95% confidence intervals.

Phase 2:

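### Reduced error pruning is planned with no pruning sample and an undefined 10% rule; with about 40 SSIs at month 4, the screening questions kept would depend largely on the random split or on unstated choices

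*Combined protocol and SAP*

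**What the plan says.** The relevant text is in the Phase 1 analysis for Aim 1 (Analysis and Outcomes). The timing is "At 4 months into Phase 1, we will assess the validity of the SSI screening protocol". The redesign is conditional: "If the sensitivity of SSI screening protocol is less than 90% or the specificity is less than 80%, we will modify and optimize" the screen. Modification step 1 then reads "We will develop maximal trees with all six screening questions, and then apply reduced error pruning". It continues with a rule that a question is dropped unless it lowers predictive error by 10%, and the final tree is picked on its general predictive performance.

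The plan names no pruning or validation sample, no split fraction and no cross-validation. It does not say whether the 10% is relative or in percentage points, or whether it is measured against the whole tree's error or one node's. The data from the following three months are assigned to a new cutoff and to reassessing sensitivity and specificity, not to pruning.

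The enrolment period is given in two ways. Subject Selection and Enrollment says "We anticipate enrolling 525 post-operative c-section patients who received surgery at KDH during the seven-month period". Study Procedures, Phase 1, says "We anticipate enrolling a minimum of 525 post-operative patients during the five-month period".

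**The concern.** Reduced error pruning, by definition, removes branches according to their error in patients who did not help grow the tree. Without such patients, the analyst must either carve a hold-out from a small number of SSIs or prune on the growing data, where error is optimistic because the tree was fitted to it.

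The tree decides which questions are removed and replaced for the rest of Phase 1. The resulting algorithm goes into Phase 2, where it determines who is referred back to the hospital in Arms 1 and 2. If the set of questions turns on an arbitrary split, or on a reading of the 10% chosen after the data are seen, the choice cannot be reproduced from the plan.

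**Working it through.** **The plan's own figure.** The inputs are 525 women, 10% loss to follow-up and 15% SSI (Study Procedures, Phase 1).
- With SSI: 525 × 0.90 × 0.15 = 70.9.
- Without SSI: 525 × 0.90 × 0.85 = 401.6.

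Both match the plan: "we expect 71 patients will have a GP-diagnosed SSI and 402 patients will not have a GP-diagnosed SSI".

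**SSIs at month 4.** Assuming even accrual, the count is 525 × 4/(enrolment months) × 0.90 × SSI rate. The plan's range for the rate is "we expect the true rate of SSI in patients receiving surgery KDH to be 10-20" per cent.

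| Accrual | Women seen | SSIs at 15% | SSIs at 10-20% |
|---|---|---|---|
| 7 months | 270 | 40.5 | 27-54 |
| 5 months | 378 | 56.7 | 38-76 |

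Women still admitted at follow-up are excluded from developing the algorithm, and refugee-camp patients are not asked to return. Both lower these counts by amounts the plan does not give.

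**Size of a hold-out.**
- One third, seven-month accrual: 40.5/3 = 13.5 SSIs, so one SSI moves sensitivity by 1/13.5 = 7.4 points.
- One third, five-month accrual: 56.7/3 = 18.9 SSIs, or 1/18.9 = 5.3 points each.

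**What 10% means in women.** A tree with no questions calls everyone non-SSI, so its unweighted error count equals the number of SSIs in the pruning sample. If the 10% is relative to that root error, then with seven-month accrual and 15% SSI:
- one-third hold-out: 0.10 × 13.5 = 1.35 women;
- one-half hold-out: 0.10 × 20.25 = 2.0 women;
- all the data: 0.10 × 40.5 = 4.05 women.

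Across both accrual texts and 10-20% SSI, hold-outs of a third to a half give 0.9 to 3.8 women. If 10% means percentage points, the margin in a one-third sample of 90 women is 9 women.

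**Illustrative simulation, unweighted errors.** There were 300 data sets of 270 women with 40 SSIs and six yes/no items. Assumed item sensitivities were 0.50-0.75 and false-positive rates 0.05-0.20. Maximal Gini trees were pruned from the bottom up with the 10% rule. The last column is the share of data sets in which removing some single woman from the pruning data changes the questions kept (61 data sets for the growing-data rows).

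| Pruned on | 10% against | Mean questions kept | All six kept | Same set on a second split | Changed by one woman |
|---|---|---|---|---|---|
| Growing data | node | 5.9 | 90% | n/a | 21% |
| Growing data | root | 3.3 | under 1% | n/a | 56% |
| One-third hold-out | node | 4.0 | 14% | 21% | 70% |
| One-third hold-out | root | 2.6 | 2% | 28% | 63% |
| One-half hold-out | node | 4.1 | 14% | 18% | 69% |
| One-half hold-out | root | 3.0 | 1% | 23% | 56% |

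**Equal class weights** (100 data sets, 40 SSI and 230 non-SSI women, similar assumed items). Pruning on the growing data kept all six questions in 99% of data sets under the node rule, and 1.6 questions on average under the root rule. The same question set came back on a second split in 31-32% with a one-third hold-out and in 81% with cross-validated cost-complexity pruning. With 57 SSI and 321 non-SSI women the figures were 27-46% and 77%. Further runs gave 12-54% for hold-out and 70-88% for cross-validation.

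**Accuracy** (mean of true sensitivity and specificity, same equal-weight run). One-third hold-out gave 0.786 (node) and 0.766 (root); cross-validated cost-complexity pruning gave 0.793. The gains are 0.793 − 0.786 = 0.007 and 0.793 − 0.766 = 0.027.

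**The case against.** A reader might infer that the choice of questions must be either unpruned or decided by one or two women. The documents do not support that.
- The 10% rule makes a split earn its place even on the growing data. Taken against root error, it prunes hard.
- The plan does not exclude cross-validated error, which would use every SSI.
- The margin of one or two women assumes a relative 10%, seven-month accrual and a hold-out of a third to a half.

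It is also fair to say that the step runs only if the 90%/80% targets are missed. Replacement questions draw on local and expert input, photo review by a GP is a second route, and month 7 brings reassessment with confidence intervals. The accuracy gain is small and rests on assumed item rates. In one unweighted run, cross-validation (0.75) beat the hold-out versions (0.69-0.73), but growing-data pruning with a node rule was slightly ahead (0.764). In another, growing-data pruning led by 0.728 to 0.714. On this view it is enough to name the error sample and define the 10%.

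Most of this stands and limits the point to reproducibility. Two parts do not remove it. The month-7 reassessment can reveal a poor screen, but it chooses the cutoff again on those data and no further redesign is scheduled. Clarifying the wording is also not enough if the clarification is a hold-out, because the dependence on the split remains.

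**Conclusion.** The concern holds as a gap in specification and stability. The method named needs data the plan does not set aside, and the 10% rule can be read in ways that keep from one or two questions to all six (the low end comes from the equal-weight runs; the unweighted run kept 3.3). With a one-third hold-out of about 13 SSIs, or about 19 under five-month accrual, the questions kept depend largely on the random split: the same set recurred in 12-54% of data sets, against 70-88% with cross-validation. Those percentages describe stability when the same women are partitioned again, not when new women are sampled.

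The accuracy gain over hold-out pruning is about 0 to 0.03 in most runs, so a markedly better screen should not be claimed. Nor does the finding undermine the randomised comparison in Phase 2; it concerns how the screen used there is chosen. The counts assume even accrual, 15% SSI and 10% loss to follow-up. All simulation figures rest on assumed item properties. The change is worth making before the month-4 assessment.

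**What to change.** In Aim 1, modification step 1, replace reduced error pruning with cost-complexity pruning. Choose the penalty by repeated 10-fold cross-validation, stratified by SSI, on all eligible women seen by month 4, and decide which questions to remove from that tree. Either drop the 10% rule or define it as a relative reduction in cross-validated error. Reconcile the five-month and seven-month enrolment texts so that the expected month-4 count is clear.

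The cost is SAP wording, standard software and slightly more computation, with no extra patients or data. The one thing given up is the 10% rule in its present form.

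### The Phase 1 tree is pruned and chosen on predictive error, with no class weights and no tie to the 90/80 target; at a 15% SSI rate this pulls towards low sensitivity

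*Combined protocol and SAP*

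**What the plan says.** Under Biostatistical and Qualitative Analysis, Phase 1, Aim 1, the screen is first a count rule: positive if at least c of six signs are present, with c taken from the ROC curve at month 4. Modification is triggered by a stated target: "If the sensitivity of SSI screening protocol is less than 90% or the specificity is less than 80" per cent.

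Modification step 1 grows a maximal tree on all six questions and applies reduced error pruning, "removing questions that do not reduce predictive error by 10" per cent. Selection follows: "We will choose optimal trees based on overall predictive properties of the pruned tree". The plan does not define predictive error or say whether the 10% is relative or absolute. It gives no priors, class weights or misclassification costs. Neither step refers back to 90/80.

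If questions are removed, new ones are proposed; step 2 adds GP photo review. At month 7 a new cutoff is set, sensitivity and specificity are re-estimated with confidence intervals, and that algorithm goes to Phase 2. No minimum performance is attached.

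On prevalence, Study Procedures, Phase 1 states: "With an estimated overall SSI rate of 15% based on existing literature". Subject Selection gives a range: "we expect the true rate of SSI in patients receiving surgery KDH to be 10-20" per cent.

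**The concern.** The target treats the two errors asymmetrically: at most 10% of infected women missed, up to 20% of uninfected women flagged. Unweighted error counts one missed infection the same as one false alarm, and at 15% prevalence there are 5.7 uninfected women for each infected one. Minimising that error favours specificity. The repair step starts when the screen falls short of 90/80, yet it optimises a quantity that can move away from the sensitivity half of that target.

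In Phase 2, Arms 1 and 2 refer only women whom the screen identifies. A less sensitive screen refers fewer infected women, which would shrink the Aim 4 contrast and leave some infected women reminded of warning signs but not referred.

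**Working it through.** **1. The plan's own figure.** The inputs are 525 enrolled, 10% loss and 15% SSI (Study Procedures, Phase 1). 525 × 0.90 = 472.5 evaluable; × 0.15 = 70.9 with SSI; × 0.85 = 401.6 without. This reproduces "we expect 71 patients will have a GP-diagnosed SSI and 402 patients will not have a GP-diagnosed SSI".

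**2. Error at the target against calling nobody infected.** Error = p(1 − sens) + (1 − p)(1 − spec). Calling nobody infected has error p.

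| SSI rate p | Nobody infected | Rule at 90/80 |
|---|---|---|
| 10% | 10.0% | 0.10×0.10 + 0.90×0.20 = 19.0% |
| 15% | 15.0% | 0.15×0.10 + 0.85×0.20 = 18.5% |
| 20% | 20.0% | 0.20×0.10 + 0.80×0.20 = 18.0% |

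Break-even: p = 0.10p + 0.20(1 − p), so p = 0.20/1.10 = 18.2%.

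**3. What pruning does to a single split at 90/80.** Its positive predictive value at 15% is 0.135/(0.135 + 0.170) = 44.3%. This is below one half, so majority vote labels both branches uninfected. The split shows no error reduction and is pruned.

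**4. Why relative or absolute matters.** At 90% sensitivity and 15% SSI, specificity must be 1 − (target error − 0.015)/0.85:
- to match calling nobody infected (15.0%): 84.1%;
- for a 10% relative reduction (13.5%): 85.9%;
- for a 10-point reduction (5.0%): 95.9%.

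**5. Where unweighted error settles.** Illustration (assumed equal-variance binormal ROC through 90/80): the minimum-error point is 51% sensitivity / 98% specificity at 10% SSI, 60% / 97% at 15% (error 8.6%) and 66% / 96% at 20%. The pull towards specificity therefore remains above 18.2%; only the comparison with calling nobody infected reverses there.

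**6. Simulated trees.** Assumptions: six conditionally independent items, 15% SSI, two-thirds of the sample to grow and one-third to prune, a 10% relative rule, and 270 women at month 4 (472.5 × 4/7, even accrual, about 40 SSIs). Study Procedures also mentions five months, which would give 472.5 × 4/5 = 378 women and 57 SSIs. Only items for which no count cutoff meets 90/80 are relevant, since otherwise the tree is not normally built. Mean results by the tree's own majority label:

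| Item sens/spec | Nearest count rules | Unweighted | Equal class weight |
|---|---|---|---|
| 50/80 | c=2: 89.1/65.5 | 21/97 | 62/79 |
| 60/80 | c=2: 95.9/65.5; c=3: 82.1/90.1 | 41/96 | 70/85 |
| 60/85 | c=2: 95.9/77.6; c=3: 82.1/95.3 | 50/97 | 74/88 |

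Items at 70/80 or 70/85 are left out: three of six gives sensitivity 93.0% with specificity 90.1% or 95.3%, which passes.

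**7. Adding the month-7 cutoff.** Items at 50/85 (c=2: 89.1/77.6, a narrow miss):
- retained items counted: 78% / 81% after unweighted pruning, against 81% / 82% after weighted;
- tree itself kept: 64% / 73% against 71% / 80%.

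With weaker assumed items, unweighted pruning kept 2.6 questions on average against 4.6.

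**8. Scale for Aim 4 (assumption).** Suppose the planned 80% return goes with 90% sensitivity, and missed women return at rate m, from 0 to the Arm 3 rate of 40%. Return among referred cases is r = (0.80 − 0.10m)/0.90, so r is 0.889 to 0.844. Each 10 points of sensitivity lost then costs 0.15 × 0.10 × (r − m) = 0.67 points (m = 40%) to 1.33 points (m = 0) of the 12% expected in Arms 1 and 2. The 3- to 7-point sensitivity gaps in step 7 are worth about 0.2 to 0.9 of the planned 6-point difference.

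**The case against.** The strongest reply is that the tree's majority label is not the final operating point. On a natural reading, the tree chooses items and the month-7 cutoff then sets the balance. Step 7 bears this out where the retained items are simply counted: the sensitivity gap falls to about 3 points. It does not remove the point, because the plan does not say whether the cutoff applies to a count or to the tree, and a later cutoff cannot restore a dropped question.

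Second, the text never says that predictive error is unweighted, and the selection phrase could take in sensitivity and specificity. That is fair. Still, unweighted misclassification is what reduced error pruning ordinarily means, nothing in the plan departs from it, and selection comes after pruning.

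Third, the plan has safeguards: replacement questions, photo review, and re-estimation with confidence intervals. A poor algorithm would be seen. The plan does not say that it would be held back.

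Fourth, weighting does not reach 90% sensitivity in these simulations, and with about 40 SSIs at month 4 one case moves sensitivity by 2.5 points. Both are true. They argue for cross-validation and modest expectations, not for the unweighted criterion.

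**Conclusion.** The concern holds in a limited form. The pruning and selection criterion is undefined and not tied to the plan's own target. In its ordinary unweighted meaning, at the planned 15% SSI rate, it scores a 90/80 screen (18.5% error) below calling nobody infected (15.0%). That ranking needs an SSI rate below 18.2%. The pull towards specificity is more general.

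Two stronger readings are tempting and not supported. One is that pruning would return a tree calling nobody infected: in the simulations this happened in under 1% to 29% of runs, depending on assumed item quality, and the ranking reverses at the top of the plan's prevalence range. The other is that a screen with sensitivity as low as the majority-label figures will enter Phase 2: that ignores the month-7 cutoff, the replacement questions and the photo step.

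The exact part is the error arithmetic. The simulated sensitivities, and the Aim 4 scale built on them, are illustrations under assumed independent items. The step matters only if the month-4 check fails.

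**What to change.** In modification step 1, state that trees are grown and pruned with equal class priors. A missed SSI then weighs 0.85/0.15 = 5.7 times a false alarm at 15% SSI (9 times at 10%, 4 times at 20%). Calling nobody infected then has 50% error and a 90/80 rule (0.10 + 0.20)/2 = 15%, so the ranking agrees with the target. Say whether the 10% is relative or absolute. Choose the final tree and cutoff by cross-validated sensitivity subject to specificity of at least 80%, and say whether the cutoff applies to a count of retained items or to the tree. It would also help to state what follows if the month-7 estimates still miss 90/80.

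The core change is two or three sentences in the analysis plan and one software option, with no new data. The price is more false referrals than under plain error, within the plan's own 80% specificity limit. Weighting does not by itself guarantee 90% sensitivity.
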